Patient-reported outcome assessments^o									
EORTC QLQ-C30, CCI	X	X						q8w (±3 days) relative to the date of Cycle 1 Day 1	
EORTC QLQ-H&N35, CCI	X	X						q4w (±3 days) relative to the date of Cycle 1 Day 1	
Other laboratory assessments and assays									
Tumor biopsy or obtain archival tumor tissue <3 years old for PD-L1 status	X ^c								
Tumor evaluation (CT or MRI) (RECIST 1.1) ^q	X	First on-treatment scan at 6 weeks (+1 week) and then q6w (±1 week) for the first 24 weeks relative to the date of randomization and then q8w (±1 week) thereafter							

CCI

Window for visits is relative to day of dosing, even if dosing is delayed, unless otherwise specified.

- ^a Cycle 1 Day 1 procedures do not need to be repeated if the same procedures were performed for screening purposes 3 days prior to Cycle 1 Day 1.
- ^b Patient visits will change from q3w to q4w after completion of chemotherapy.
- ^c Informed consent of study procedures and tumor sample acquisition may be obtained prior to the 28-day screening window, if necessary, in order to permit tumor sample acquisition and analysis prior to randomization. PD-L1 testing will be done from a newly acquired tumor biopsy (preferred) or archival tissue (<3 years old).
- ^d Pre-dose and as clinically indicated before every infusion or administration.
- ^e Any clinically significant abnormality detected requires a confirmatory ECG.
- ^f HPV status testing may be performed for oropharyngeal tumors only. Local testing is acceptable and preferred. If HPV status is unknown or unavailable locally, a newly acquired or archived tumor sample must be submitted for central testing at a reference laboratory as described in the Laboratory Manual.
- ^g To be collected q3w prior to the start of infusion and as clinically indicated. Electrolytes should be monitored with cetuximab therapy as per institution guidelines.

- h If screening assessments are performed within 3 days prior to Day 1 (first infusion day), they do not need to be repeated at Day 1.
- i If the patient does not complete treatment through Cycle 5, TSH should be obtained after the patient's last cycle.
- j Free T₃ or free T₄ will only be measured if TSH is abnormal or if there is clinical suspicion of an AE related to the endocrine system.
- k For women of childbearing potential only. A pregnancy test must be performed within 7 days before Cycle 1 Day 1. A urine or serum pregnancy test is acceptable.

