SoC (EXTREME): Patients in the SoC treatment arm will receive the EXTREME regimen consisting of a maximum of six 3-week cycles of cetuximab, a platinum, and 5FU, with continuation of cetuximab. Patients in this arm will receive either cisplatin (at a dose of 100 mg/m² of body surface area on Day 1) or carboplatin (at an AUC of 5 mg/mL/min on Day 1), at the discretion of the Investigator and an infusion of 5FU (at a dose of 1000 mg/m²/day on Days 1 through 4 of every 3-week cycle). Cetuximab will be administered at an initial dose of 400 mg/m² on Cycle 1 Day 1, followed by subsequent weekly doses of 250 mg/m². Weekly monotherapy with cetuximab should continue after the completion of up to 6 cycles of chemotherapy in patients who achieve SD or better. Any drug within the triplet regimen (cetuximab, a platinum, and 5FU) can be discontinued at any time due to toxicity at the discretion of the Principal Investigator.

Patients will be treated with MEDI4736 + tremelimumab combination therapy, MEDI4736 monotherapy, or SoC until confirmed PD (unless, in the Investigator's opinion, the patient continues to receive benefit from the treatment and after discussion with the Sponsor), initiation of alternative cancer therapy, unacceptable toxicity, withdrawal of consent, or another treatment discontinuation criterion is met (see Section 3.9). Patients with PD in target lesions after objective response are not eligible to continue treatment.

Disease progression requires confirmation for patients receiving IMT. All scans showing PD by RECIST 1.1 should be confirmed, preferably at the next scheduled visit and no earlier than 4 weeks after the preceding assessment of PD in the absence of clinical deterioration. Disease progression in patients in the SoC arm should be confirmed by a scan obtained no earlier than 4 weeks after the initial assessment of PD and preferably at the next scheduled imaging visit, if clinically feasible. Treatment in all arms will continue between the assessment of progression and its confirmation. If progression is not confirmed, then the patient should continue receiving study treatment and participating in study assessments. If progression is confirmed and the patient continues to receive some clinical benefit, treatment may be continued at the Investigator's discretion. Patients with clinical evidence of progression who do not meet PD criteria by RECIST 1.1 should have radiographic documentation of PD.

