### 3.3.2 Treatment exposure

Exposure will be defined separately for MEDI4736 monotherapy, MEDI4736 on the MEDI4736+ tremelimumab combination arm, tremelimumab on the MEDI4736+tremelimumab combination arm, and also separately for cetuximab, a platinum [carboplatin or cisplatin], and 5FU on the standard of care arm for the initial period of treatment and for the retreatment period as follows:

Total (or intended) exposure of MEDI4736 (monotherapy)

- Total (or intended) exposure is defined as the total treatment period from first dose date of study drug to earliest of “last dose date of study drug + 27 days” or death date or DCO.

Total (or intended) exposure of MEDI4736 (combination)

- Total (or intended) exposure is defined as the total treatment period from first dose date of study drug to the earliest of “last dose date of study drug + 27 days” or death date or DCO regardless of tremelimumab being re-started or not.

Total (or intended) exposure of tremelimumab (combination)

- Total (or intended) exposure is defined as the total treatment period from first dose date of study drug to the earliest of “last dose date of study drug + 27 days” or death date or DCO. This will include the sum of the duration in the 2 tremelimumab periods (i.e., initial period and re-treatment) but excluding the count of time between the 2 periods (for example, the duration would sum up to 6 months if they did 3 months in each case even if the 2 periods were separated by several months).

Actual exposure of MEDI4736/tremelimumab

- Actual exposure is defined as above, but excluding total duration of dose delays. Actual treatment duration for tremelimumab will be derived similarly as was done by total exposure, that by combining the periods of tremelimumab and summing up the delays in each period.

Total (or intended) exposure for the SOC regimens (cetuximab, a platinum [carboplatin or cisplatin], and 5FU)

- The total (or intended) exposure for the individual SOC regimens will be calculated according to the dose schedule required for each SOC regimen as follows:
  - (a) Cetuximab: Total (or intended) exposure is defined as the total treatment period from first dose date of study drug to the earliest of “last dose date of study drug + 6 days” or death date or DCO
  - (b) Platinum and 5FU: Total (or intended) exposure is defined as the total treatment period from first dose date of study drug to the earliest of “last dose date of study drug + 20 days” or death date or DCO

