The total (or intended) exposure will also be summarised by combining the SOC treatments together. The following rules will be applied for SOC total

- Total (or intended) exposure is defined as the total treatment period from first dose date of study drug to the earliest of “last dose date of YY SoC drug + xx days” or death date or DCO, xx depends on whether the patient was still receiving platinum or 5FU, or only on cetuximab:
  - if last dose of cetuximab is  $\geq 14$  days after last dose of platinum and 5FU, then YY=cetuximab and xx= 6 days
  - if last dose of cetuximab is  $< 14$  days after last dose of platinum and 5FU, then YY=platinum and xx= 20 days

Actual exposure will not be calculated for SOC.

Dose reductions are not permitted per the CSP for the immunotherapy agents (MEDI4736 or MEDI4736+tremelimumab). The actual exposure calculation makes no adjustment for any dose reductions that may have occurred.

Exposure will also be measured by the number of cycles received. For the immunotherapy arms, a cycle corresponds to a 4-week treatment; for SOC, a cycle corresponds to a 3-week treatment. If a cycle is prolonged due to toxicity, this should still be counted as one cycle. A cycle will be counted if treatment is started even if the full dose is not delivered. Each immunotherapy agent will be measured in terms of number of doses given.

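### The combined SoC exposure rule in SAP 3.3.2 has no 5FU branch, so it shortens or leaves undefined the exposure of patients who drop platinum, continue 5FU, and stop cetuximab at about the same time as 5FU or before it

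*SAP*

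**What the plan says.** SAP 3.3.2 first defines exposure for each SoC drug. Each definition takes the earliest of three dates: death, data cut-off (DCO), and a date counted from the drug's last dose. For cetuximab ("a) Cetuximab: Total (or intended) exposure is defined as the total treatment period from first dose date of study drug to the earliest of") that third date is 6 days after the last dose. For the chemotherapy drugs ("b) Platinum and 5FU: Total (or intended) exposure is defined as the total treatment period from first dose date of study drug to the earliest") it is 20 days after the last dose.

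It then defines one combined SoC total. The end date is the last dose of a drug called YY plus xx days, again capped by death or DCO. The lead-in says that "xx depends on whether the patient was still receiving platinum or 5FU, or only on cetuximab". Two branches follow:

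- Last cetuximab dose 14 or more "days after last dose of platinum and 5FU, then YY=cetuximab and xx= 6 days".
- Last cetuximab dose fewer than 14 "days after last dose of platinum and 5FU, then YY=platinum and xx= 20 days".

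No branch sets YY to 5FU.

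Protocol 7.2.1 states: "Any drug within the triplet regimen (cetuximab, a platinum, and 5FU) can be discontinued at any time due to toxicity". Protocol 1.2.4 says the same. A patient on 5FU and cetuximab without platinum is therefore foreseen.

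Total exposure is a planned summary for SoC (SAP 4.2.19). Actual exposure is not calculated for SoC (SAP 3.3.2). SAP 4.2.13.1 also plans adverse event (AE) rates per 100 patient-years, with total drug exposure as the denominator.

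**The concern.** The lead-in treats platinum and 5FU as alternatives: being on either one should put the patient in the chemotherapy branch. The branch itself then takes its date from platinum alone. For a patient who dropped platinum some cycles ago but still received 5FU, the end of SoC treatment is set by a drug no longer being given.

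When the rule misfires it can only shorten exposure, because the last platinum dose plus 20 days is never later than the latest of the three per-drug end dates. It also affects only the control arm. For the combination arm, SAP 4.2.13.1 states that the AE rate uses the very last dose of either drug. Where the SoC total is the denominator, the count of patients with an event is unchanged and the time at risk shrinks, so the SoC rate rises relative to the immunotherapy arms.

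**Working it through.** The plan gives no exposure figure to reproduce. The check applies the rule to the protocol schedule.

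**Inputs**

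- Platinum on Day 1 and 5FU on Days 1 to 4 of each 21-day cycle, up to six cycles; weekly cetuximab (Protocol Table 3 and section 7.2.1).
- Cycle start days: 1, 22, 43, 64, 85, 106 (Table 3).
- Last 5FU in cycle 6: 106 + 3 = day 109.
- Last cetuximab in cycle 6 (18th weekly dose): 1 + 7 × 17 = day 120.
- Per-drug end dates (SAP 3.3.2): platinum + 20, 5FU + 20, cetuximab + 6.

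The first dose is on day 1, so exposure in days equals the end day.

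**Full triplet for six cycles.** Cetuximab ends 120 − 109 = 11 days after the last chemotherapy dose, so the platinum branch applies: 106 + 20 = day 126 = 6 × 21. The rule works when platinum is not dropped.

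**What the 14-day cut is for.** 14 + 6 = 20. The switch falls where last cetuximab + 6 equals last chemotherapy + 20, so the rule is built to take the later of two end dates. 5FU was left out of one of them.

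**Platinum dropped after cycle 2; 5FU and cetuximab through cycle 6.**

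- Combined rule: 22 + 20 = day 42.
- Per-drug rules: platinum day 42; 5FU 109 + 20 = day 129; cetuximab 120 + 6 = day 126.
- The combined total is shorter than two of its own components and ends 109 − 42 = 67 days before the last 5FU dose.
- Against day 126, this patient's exposure is understated by a factor of 126 / 42 = 3.0.

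**All stopping points, with 5FU and cetuximab through cycle 6**

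| Platinum cycles given | Last platinum day | Rule ends on day | Short of day 126 | Short of day 129 |
|---|---|---|---|---|
| 1 | 1 | 21 | 105 | 108 |
| 2 | 22 | 42 | 84 | 87 |
| 3 | 43 | 63 | 63 | 66 |
| 4 | 64 | 84 | 42 | 45 |
| 5 | 85 | 105 | 21 | 24 |
| 6 | 106 | 126 | 0 | 3 |

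In the first five rows the end date falls before the last 5FU dose on day 109.

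**5FU stopped sooner.** Platinum for two cycles, 5FU and cetuximab for three: last 5FU 43 + 3 = day 46, last cetuximab 1 + 7 × 8 = day 57, gap 11 days. The rule gives day 42; cetuximab alone runs to 57 + 6 = day 63. The shortfall is 21 days (24 against the 5FU end date of day 66).

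**Cetuximab maintenance.** Same patient with platinum for two cycles and 5FU for six, but last cetuximab on day 162: 162 − 109 = 53 days, which is 14 or more. The cetuximab branch gives 162 + 6 = day 168. Nothing is lost.

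**The other reading of the condition.** If the 14-day test must hold for platinum and for 5FU separately, the two-cycle platinum patient has gaps of 120 − 22 = 98 and 120 − 109 = 11 days. One passes and the other fails, so neither branch applies. On this reading even the full six-cycle patient falls between the branches (120 − 106 = 14; 120 − 109 = 11). That suggests it was not intended, but the text does not exclude it.

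**The case against.** The best defence is that platinum in the second branch is shorthand for the chemotherapy component. The per-drug rule groups platinum and 5FU under one 20-day convention, and the lead-in contrasts either drug with cetuximab alone. This may well be what was meant, but the SAP does not say so, and a programmer coding the text literally gets day 42. The SAP 3.3.2 paragraph on permanent discontinuation during a dose interruption points to the last recorded administration. It covers stopping between cycles or during a delay, names no component, and does not settle YY.

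The limits on impact stand. Safety is descriptive (SAP 4.2.13). The main AE tables are counts and percentages with windows tied to discontinuation of treatment, so they do not use this variable. Exposure for each SoC drug is also defined separately, so a truncated total could be noticed. Patients who switch from cisplatin to carboplatin, whom SAP 3.3.3 foresees, remain on a platinum and are unaffected.

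A reader might infer that every patient who drops platinum loses exposure. The protocol does not support that: patients with stable disease or better continue weekly cetuximab after chemotherapy, and once this reaches 14 days beyond both drugs the cetuximab branch gives the right date.

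A reader might also see an error in the cycle count, since the SAP says that "for SOC, a cycle corresponds to a 3-week treatment" while Protocol Table 3 moves to 4-weekly from Cycle 7. The Table 3 footnote reads "Patient visits will change from q3w to q4w after completion of chemotherapy", which concerns visits, and cetuximab stays weekly throughout. That is a choice of reporting unit.

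**Conclusion.** The rule is wrong as written for a defined group: platinum dropped, 5FU continued, and last cetuximab fewer than 14 days after the last 5FU dose or before it. For them the SoC total is dated from an old platinum dose or, on the alternative reading, may have no end date.

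The loss is 21 to 105 days against day 126. This assumes on-schedule dosing, 5FU and cetuximab through cycle 6, and platinum stopped after cycle 5 down to cycle 1. It is smaller if 5FU stops sooner, and zero if cetuximab continues 14 days or more beyond both drugs.

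A reader might want to turn this into a percentage bias in the SoC arm. The documents give neither the number of such patients nor the mean SoC exposure, so no arm-level figure can be supported. The direction is known: SoC exposure is understated, and SoC AE rates per 100 patient-years are inflated where this total is the denominator. SAP 4.2.13.1 does not say explicitly which SoC duration it uses. Overall survival and the other efficacy analyses are untouched.

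**What to change.** Replace the two branches in SAP 3.3.2 with one definition: SoC total exposure runs from the first dose of any SoC drug to the earliest of death, DCO, or the latest of the three per-drug end dates already in that section (last platinum + 20 days, last 5FU + 20 days, last cetuximab + 6 days). This removes both the truncation and the undefined case. State in SAP 4.2.13.1 that this total is the SoC denominator, if that is intended.

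The cost is one paragraph of SAP text and a small programming change, with no new data. There is one side effect. Because 5FU is given on Days 1 to 4, a patient with the full triplet for six cycles moves from day 126 to 109 + 20 = day 129. If the sponsor prefers to keep day 126, 5FU exposure can end with the 21-day cycle in which 5FU was last started (106 + 20 = 126). The same convention should then be used in the per-drug 5FU rule, so that the total is never shorter than one of its components.

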### **Patients who permanently discontinue during a dose interruption**

If a decision is made to permanently discontinue study treatment in-between cycles or during a cycle delay then the date of last administration of study medication recorded will be used for the calculation of exposure.

### **Calculation of duration of dose delays (for actual exposure):**

MEDI4736 (monotherapy):

- For all dosing dates:  
Total duration of dose delays= Sum of (Date of the dose - Date of previous dose – 28 days)  
Thus, if no delays were encountered, the duration would sum up to 0, since infusions were done every four weeks.

MEDI4736 (given in combination):

- Duration of dose delays= Sum of (Date of the dose - Date of previous dose – 28 days); this will include re-treatment period as was done for the exposure derivation

Tremelimumab (given in combination):

- Duration of dose delays= Sum of (Date of the dose - Date of previous dose – 28 days)

### 3.3.3 Dose intensity

Dose intensity will be derived for the initial treatment period and the re-treatment period for the immunotherapy agents. It will also be derived for each of the SOC agents (cetuximab, a platinum [carboplatin or cisplatin], and 5FU). Relative dose intensity (RDI) is the percentage of the actual dose delivered relative to the intended dose through to treatment discontinuation.

Relative dose intensity (RDI) will be defined as follows for MEDI4736, tremelimumab and all Standard of Care therapy:

- $RDI = 100\% * d/D$ , where d is the actual cumulative dose delivered up to the actual last day of dosing and D is the intended cumulative dose up to the actual last day of dosing. D is the total dose that would be delivered, if there were no modification to dose or schedule.

For patients who started cisplatin and later switched to carboplatin, the last day of dosing for both the intended and actual dosing for cisplatin will be the last day prior to switching to carboplatin, and for carboplatin, day 1 will be the first day of dosing of carboplatin in these patients (e.g., if the first day of carboplatin was given on study day 22, then day1 for carboplatin=study day 22, etc). If patients switch from carboplatin to cisplatin in any way other than once from cisplatin to carboplatin, no RDI will be calculated for them.

In cases where the units for the recorded dose is different from the planned dose, the following conversion should be applied when feasible:

1. 100mg/m^2 of body surface area: If the recorded dose is in mg instead of mg/m^2, height and weight (use most current weight) will be used to derive body surface area using Du Bois formula)
2. AUC of 5 mg/mL/min: If the recorded dose unit is in mg instead of AUC then the following algorithm should be used to convert doses in mg to AUC

1.  $GFR = Sex * \left( \frac{(140 - Age(years))}{(Creatinine(mg/dL))} \right) * (Weight(kg)/72)$ , values for sex:  
Male=1, Female=0.85

2.  $TargetAUC = Carboplatin Dose (mg)/(GFR + 25)$

3.  $CarboplatinDose = TargetAUC * (GFR + 25)$

Note: For MEDI4736 monotherapy in the combination arm and tremelimumab, RDI would use the intended dose for the 2 periods (initial and re-treatment periods) combined.

### 3.3.4 Laboratory data

Laboratory data will be collected throughout the study, from screening to the follow-up visits as described in Tables 2, 3 and 4 of the CSP. Blood and urine samples for determination of hematology, clinical chemistry, and urinalysis will be collected as described in Section 5.2.1

of the CSP. For derivation of baseline and post baseline visit values considering visit window and how to handle multiple records, derivation rules as described in Section 3.3.7 below will be used.

Change from baseline in hematology and clinical chemistry variables will be calculated for each post-dose visit on treatment. CTCAE grades will be defined at each visit according to the CTCAE grade criteria using local or project ranges as required, after conversion of lab result to corresponding SI units. The following parameters have CTCAE grades defined for both high and low values: Potassium, Sodium, Magnesium, Glucose and Corrected calcium so high and low CTCAE grades will be calculated.

Corrected Calcium will be derived during creation of the reporting database using the following formula:

$$\text{Corrected calcium (mmol/L)} = \text{Total calcium (mmol/L)} + ([40 - \text{Albumin (G/L)}] \times 0.02)$$

Absolute values will be compared to the project reference range and classified as low (below range), normal (within range or on limits of range) and high (above range).

The maximum or minimum on treatment value (depending on the direction of an adverse effect) will be defined for each laboratory parameter as the maximum (or minimum) post-dose value at any time.

Local reference ranges will be used for the primary interpretation of laboratory data. The denominator used in laboratory summaries of CTCAE grades will only include evaluable patients, in other words those who had sufficient data to have the possibility of an abnormality.

For example:

- If a CTCAE criterion involves a change from baseline, evaluable patients would have both a pre-dose and at least 1 post-dose value recorded.
- If a CTCAE criterion does not consider changes from baseline, to be evaluable the patient needs only to have 1 post dose-value recorded.

